Our proposed theory-derived intervention is guided by theoretical constructs from the self-efficacy theory. Self-efficacy, one's confidence in the ability to perform particular behaviors, influences the performance of those behaviors, which in turn impacts health outcomes. Enactive mastery experiences, verbal persuasion, vicarious experiences, and physiological/ emotional status are the four principle sources of self-efficacy beliefs. Evidence illustrates that physical activity interventions designed based on self-efficacy concepts

effectively promote physical activity in older adults. The personalized behavioral intervention, which includes physical activity training, exercise prescription, goal setting, phone coaching, consultation, and feedback, real-time physical activity self-monitoring, interactive prompts and feedback with smartwatch, and weekly financial incentives will provide older adults with a stronger sense of self-efficacy. This will engage them in physical activity.

4. Study Procedures

Overview of study design: This is a two-group randomized controlled trial to test the effectiveness of a 12-week personalized behavioral intervention implementing smartwatch technology in promoting physical activity, pain, and sleep in older adults in comparison with a control group. We aim to enroll 20 eligible participants in one years and complete the study in 18 months. Length of a subject's participation time in study will be 16-18 weeks in total, which includes 2-3 week of screening and pre-intervention data collection, 12-week intervention/control period, and 2-3 week post-intervention data collection. It is an unblinded trial. Due to the nature of the intervention (ongoing communication between research team and participants), it is impossible to blind the group assignment from the participants and the research team.

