The personalized circadian-based activity guideline will be developed based on the individual's typical daily circadian profile, functional status, and preference for exercise. We will advise participants to take afternoon naps (<90 minutes) and avoid napping after 4pm and before 8pm. The research team will work with a certified exercise trainer to develop the personalized physical activity plan for each subject. An afternoon nap of the optimal duration will be advised as healthy napping. All participants will be instructed to nap during this timeframe and to avoid any naps at other times of the day, especially in early evening. The individual's typical circadian profile will be calculated from the two-week baseline Actigraph data. The participant will receive a 30-minute instruction session from the research team session to provide instructions of how to follow the personalized activity guidance and use the study devices. A smartwatch (Fitbit Versa) and a paired smartphone (if the participant does not have a smart phone) will be distributed to participants.

In person training: Participants will receive a 2 or 3 1-hour in person education sessions with the exercise trainer which includes a 20-minute general education on exercise in older adults and a 40-minute education on personalized exercise and participating the study intervention. Session 1 will be within one week after the baseline; Session 2 will be scheduled 2-3 weeks after session 2. All participants in the intervention group will have session 1 and session 2. If the trainer feels the participant need another session to perform the exercise independently, session 3 will then be scheduled as needed. To facilitate the participant's exercise at home, we will provide a set of dumbbell and resistance band for them to use during the study. The education session will be designed using materials from the Go4Life program from the National Institute on Aging (<https://go4life.nia.nih.gov>). The participant will receive a copy of Go4Life program book and can find instructions for all selected exercise in the program book.

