Baseline data collection: After randomization, the research team will distribute an Actigraph to each eligible participant and instruct them to wear it on his/her non-dominant wrist day and night for 14 consecutive days. At the same time, the participants will be instructed to fill out a two-week sleep diary during the days they wear the Actigraph. Pre-intervention (baseline) data collection will take about 45-60 minutes. A research team member will interview eligible participants (up to 30 minutes) for age, race, education, height, weight, life style (tobacco & alcohol use), depression, pain, fatigue, self-reported physical activity, Activity of daily living, self-reported sleep quality, pain, medication use (antidepressant, benzodiazepine, pain and sleep medication), and medical conditions. The research assistant with Phlebotomy training will collect blood sample (5-10ml) from participants.

Post-intervention data collection: After the intervention or control period, a research team member will mail an Actigraph and a two-week sleep diary to the participant's home and contact the participants by phone to provide instructions. The participant will wear the Actigraph and fill out the sleep diary for 2 weeks. A research team member will schedule a meeting with the participant after the Actigraph session to collect post-intervention data. At the meeting, the participants will provide blood sample and be assessed for pain, depression, level of physical activity, and other measures that were collected at screening and pre-intervention following the same procedures. In addition, the participant will be interviewed individually for his/her perspective and experience of the intervention at the meeting for post- intervention data collection. The conversations will be audio recorded and field notes will be taken by a research team member during the interview. We estimate each interview will last no more than 30 minutes. The participant will be asked to answer open-ended questions about the participant's experience of working with smartwatch and the intervention. The voice recordings will be sent to the Production Transcripts for transcription (<https://www.productiontranscripts.com/>). Production Transcripts is a full-service transcription company that specializes in medical and academic research and has a BAA with Johns Hopkins.

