Data management: We will use the REDCap data entry and management system. Data from screening, baseline, intervention sessions, and post-intervention data collection will be entered into forms that the data manager will check for completeness and appropriateness. The data manager will send reports of missing or inappropriate entries to the PI every week for clarification and resolution. **Data that cannot be stored on the REDCap will be stored at either a locked cabinet at the research coordinator (MoCA cognitive screening) / assistants' offices at the JHU School of Nursing or at a folder as electronic files on the JHU box (actigraph data and cognitive assessment, and fitabase data) that could only be accessed by the study team.**

Measurement

Sleep Measures: We will use the Actiwatch to objectively assess nocturnal sleep in terms of total nocturnal sleep time, sleep latency, and wake after sleep onset (WASO); the smartwatch cannot be used to measure sleep due to its need for overnight charging. The Pittsburgh Sleep Quality Index, Epiworth Sleepiness Scale and Insomnia severity index will be used for subject screening and assessing sleep quality subjectively. A two-week sleep diary will be used to confirm Actiwatch-based nocturnal sleep. It will provide information on nap frequency and duration, as well as nocturnal sleep duration. Total nocturnal sleep time is the primary sleep measure, and all others are considered secondary.

Pain Measures: Presence of pain will be determined by affirmative answers to both of the following questions: (1) "Are you currently troubled by physical pain, either all the time or on and off?" and (2) "Has this pain persisted for at least 3 months?" [13]. Older adults answering yes to both questions will then be asked to specify the duration of pain and the pain sites. Pain intensity, severity, and interference with daily life will be measured by two instruments: (1) The brief pain inventory (locations and severity of pain) and (2) PROMIS pain measures (pain intensity, interference, and behaviors). Pain Self-Efficacy will be measured by the Chronic Pain Self-Efficacy Scale.

Fatigue will be assessed by the FACIT Fatigue Scale.

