7.1. Sample characteristics: We will compare the values of demographic and baseline clinical variables between the two study arms using t-tests or Mann-Whitney U-tests for continuous variables and chi-squared or Fisher’s exact tests for categorical measures. This analysis will both describe the overall study sample and confirm that randomization resulted in the expected balance between covariates of interest;

7.2 Descriptive analysis will be used to describe the feasibility data;

7.3 Preliminary efficacy: Repeated Measures ANOVA will be performed to examine if the proposed intervention increases the participants’ proposed outcomes compared to the control arm. Analyses will examine the interaction (Time × Group) to access whether there are differences in changes in outcome variables between the two arms. The initial effect size of the intervention will be determined based on results of pain outcomes.

8. Risks

Minimal risks to study participants are expected. There is minimal risk associated with physical activity. We will explain associated risk to the participants. In very rare occasions, the subject may fall or get

injured during physical activities. These adverse events should be minimized by using personalized physical activity plans, which will be developed/designed by the exercise trainer to be most suitable for the subject based on the subject's personal features. Some environmental factors (e.g. weather) may impact on the participant's safety when they perform physical activity outside. We will advise participants of this safety information during the exercise intervention. For example, we will advise them to perform indoor physical activities in the following weather conditions: temperature lower than 32°F or higher than 90°F, rainy, snowy or heavy windy weather. We will also advise them to hydrate during performing physical activity and hot weather. The activity intervention will be based on an existing NIH-funded activity protocol for older adults. Finally, the study participant's primary care provider will be contacted to confirm that the study participant can safely engage in the activity regimen.

Subjects may experience psychological reactions to completing the questionnaire data and cognitive tests. Since the questions are benign, the risk is minimal.

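### The baseline Actigraph and sleep diary start after randomisation in an unblinded trial, so knowledge of the arm can affect the baseline that the Time × Group analysis subtracts

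*Combined protocol and SAP*

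**What the plan says.** All of the following is in the combined protocol and SAP.

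- **Section 4, Randomization.** Participants found eligible at screening are allocated 1:1 in blocks of 4. The paragraph does not say when the allocation is disclosed.
- **Section 4, Baseline data collection.** "After randomization, the research team will distribute an Actigraph to each eligible participant", to be worn for 14 days. The diary covers the same days: "At the same time, the participants will be instructed to fill out a two-week sleep diary during the days they wear the Actigraph". The baseline interview (pain, sleep quality, fatigue, depression) and the blood draw come under the same heading but have no separate timing relative to randomisation.
- **Section 4, Overview of study design.** The trial is unblinded: "it is impossible to blind the group assignment from the participants and the research team".
- **Section 4, Measurement, Sleep Measures.** "Total nocturnal sleep time is the primary sleep measure". It is recorded by the wrist device.
- **Section 4, Intervention description and In person training.** The participant's "typical circadian profile will be calculated from the two-week baseline Actigraph data". For training, "Session 1 will be within one week after the baseline".
- **SAP 7.3.** A repeated measures ANOVA examines the Time × Group interaction "to access whether there are differences in changes in outcome variables between the two arms". It adds: "The initial effect size of the intervention will be determined based on results of pain outcomes".

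**The concern.** A baseline serves its purpose when allocation cannot have influenced it. Here the order is screening, randomisation, then two weeks of recording, in a trial where the arm is said not to be concealable. A participant who knows that an activity programme is coming may already change activity, naps or bedtime; one who knows they are a control may report differently. A wrist device does not prevent this, because it records behaviour, and behaviour can respond to the allocation. The diary is self-reported.

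Three uses of the baseline are exposed:

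- The Time × Group test in SAP 7.3 subtracts it.
- The pilot's initial effect size is taken from the pain outcomes. The pain interview falls under the same post-randomisation heading, so exposure of the pain baseline is probable, though not stated.
- SAP 7.1 uses baseline comparisons to confirm that randomisation balanced the arms. Variables measured after a known allocation cannot show that cleanly.

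There is also an attrition point. Anyone lost during the 14 days is already randomised but has no complete baseline. With 20 participants, each such loss is 1/20 = 5% of the sample.

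**Working it through.** **Step 1: sequence.** Read together, the section 4 paragraphs give: screening; randomisation of those eligible; Actigraph and diary for 14 days; training session 1 after baseline. Training is delayed until baseline is done, but knowledge of the arm is not. No part of the document delays disclosure.

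**Step 2: is early allocation needed?** The personalised plan rests on a circadian profile computed from the two-week baseline recording, so it cannot be finished until baseline ends. Session 1 also follows baseline. Nothing described for the baseline period depends on the arm.

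**Step 3: how a shift enters the estimate.** With two time points, the Time × Group estimate is

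(post − baseline) in the intervention arm − (post − baseline) in the control arm.

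Let *d* be the arm-related baseline shift in SD units (intervention minus control, positive for improvement), and let *p* be the fraction still present at follow-up. The bias is then −(1 − *p*)*d*: the full −*d* if the shift is confined to baseline, half of it if *p* = 0.5, and zero if it persists fully.

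**Step 4: inputs.** From the documents: 20 participants at 1:1, so 10 per arm. Assumed, because the documents give none of them: two-sided 5% test; equal SD at both times; correlation ρ between baseline and follow-up of 0.3, 0.5 or 0.7; *d* of 0.2 or 0.5 SD; a true effect of 1.0 SD for the power illustration. There is no figure of the plan's own to reproduce.

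**Step 5: standard error.** SE = √[2(1 − ρ) × 2/10] = 0.529, 0.447 and 0.346 SD for ρ = 0.3, 0.5 and 0.7. A 0.2 SD shift is therefore 0.2/0.529 = 0.38 to 0.2/0.346 = 0.58 of a standard error.

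**Step 6: error rates with no true effect.** Rejection probability comes from the noncentral t with 18 df, noncentrality = net shift/SE and critical value 2.101.

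| Shift at baseline | Persistence | Net shift | ρ = 0.3 | ρ = 0.5 | ρ = 0.7 |
|---|---|---|---|---|---|
| 0.2 SD | none | 0.2 SD | 6.5% | 7.1% | 8.5% |
| 0.2 SD | half | 0.1 SD | 5.4% | 5.5% | 5.9% |
| 0.5 SD | none | 0.5 SD | 14.6% | 18.5% | 27.7% |
| 0.5 SD | half | 0.25 SD | 7.3% | 8.3% | 10.5% |
| any | full | 0 | 5.0% | 5.0% | 5.0% |

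A simulation of the baseline-only case (200,000 trials per cell) gave a bias within 0.002 SD of the shift and error rates within 0.001 of these.

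**Step 7: direction.** Suppose the intervention arm improves in anticipation and the gain is confined to baseline. False findings in favour of the intervention fall from 2.5% to 0.6–1.0% (0.2 SD) or 0.04–0.2% (0.5 SD). False findings against it rise to 5.5–7.9% or 14–28%. The opposite shift reverses these.

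**Step 8: power.** For a true effect of 1.0 SD, power is 43%, 56% and 78% at the three correlations. A 0.2 SD anticipatory gain confined to baseline leaves a net 1.0 − 0.2 = 0.8 SD, with power of 30%, 40% and 59%. If half of it persists, the net effect is 1.0 − 0.1 = 0.9 SD, with power of 36%, 48% and 69% by the same formula.

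**The case against.** The strongest reply is that exposure is inferred from silence. No sentence says participants learn their arm before the 14-day wear, and the reason given for not blinding is the continuing contact during the intervention, which has not begun. Staff might in practice hold the allocation back. It is right that disclosure timing is unspecified. But the plan calls the trial unblinded without qualification and contains no rule that would keep the arm back, so the baseline is unprotected if the plan is followed as written.

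Other points stand in part:

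- The measures explicitly timed after randomisation are the Actigraph and the diary. The effect size comes from pain, whose interview timing is not separately stated. The firm claim is therefore about the sleep baseline; the pain baseline is a probable extension.
- An insomnia score above 7 is an inclusion criterion (section 5), so that score should exist before randomisation. This does not protect the Actigraph, diary or pain baselines.
- Participants know their arm at follow-up too, so some persistence is plausible. The half-persistence rows may then be more realistic than the baseline-only rows, and at 0.2 SD they are close to nominal.
- This is a 20-person pilot whose first objective is feasibility. SAP 7.2 is unaffected, and reordering baseline would not remove bias from unblinded follow-up reports.

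These points limit the likely size of the problem. They do not supply a reason for the present order.

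**Conclusion.** The concern holds. As written, baseline recording of the primary sleep measure follows randomisation in an unblinded trial, with no rule withholding the arm, and that baseline feeds directly into the SAP 7.3 test. The ordering is certain. Whether a shift would occur, how large it would be and which way it would run cannot be known from the documents.

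Under the assumptions listed, a 0.2 SD shift raises two-sided error to between 5.4% (half persisting, ρ = 0.3) and 8.5% (baseline only, ρ = 0.7). At 0.4–0.6 of a standard error, that is modest against sampling noise in a trial of this size. A 0.5 SD shift does more damage, but nothing in the documents supports or excludes it. The case for acting rests mainly on the fact that the weakness is avoidable at almost no cost, and that analysis cannot reliably remove a bias of unknown size and sign afterwards. It does not invalidate the pilot.

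**What to change.** **Preferred.** In section 4, complete the baseline interview, blood draw, and 14-day Actigraph and diary before randomising. Change the opening of the Baseline data collection paragraph from after to before randomisation, and move the Randomization paragraph to follow it.

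**Minimum.** Keep the order, but add a sentence that the arm is not disclosed to participants or to staff collecting baseline data until the interview is done and the Actigraph and diary have been returned. In that case, also report by arm how many randomised participants did not complete baseline.

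**Cost.** Protocol wording only; visits, devices and the target of 20 are unchanged. Under the preferred version a few people may leave before randomisation, so slightly more may need to be screened to randomise 20. The minimum version avoids that, but someone other than the baseline assessor must hold the allocation for about two weeks. Either version takes arm-related baseline bias to zero, so baseline no longer moves the test from its nominal 5%.

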Study Protocol and Statistical Analysis Plan

Title: A Personalized Behavioral Intervention for Older Adults with Musculoskeletal Pain and Sleep Complaints

NCT03921840

Date: 9/1/2020

1. Abstract

It is well recognized that physical activity/exercise is an effective intervention to improve sleep, reduce pain and improve function in a variety of pain conditions. Traditional interventions to increase physical activity are challenging in older adults due to extensive staffing requirements and low adherence. We plan to conduct a pilot trial in a cohort of older adults (without dementia) with both chronic musculoskeletal pain and nocturnal sleep complaints to test the effectiveness of a 12-week personalized behavioral intervention (compared to a control group) embedded within a smartwatch application in older adults. 20 cognitively intact elders will be enrolled and randomly allocated to intervention or control group. Participants in the intervention arm will receive a 2-hour in person education session, and personalized, circadian-based activity guidelines, with real time physical activity self-monitoring, interactive prompts, biweekly phone consultation with the research team, and financial incentives for achieving weekly physical activity goal. The control group will receive general education on physical activity in older adults and continue their routine daily activity for 12 weeks.

2. Objectives

This study aims to examine 1) the feasibility and acceptability of a personalized behavioral intervention implementing mobile health technology for promoting pain, sleep, and mood in older adults with chronic pain and sleep complaints. 2) The preliminary efficacy of the study on pain and sleep outcomes

3. Background

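### The trial is said to test promotion of physical activity against control, but the only activity measure in both arms is unblinded self-report, although both arms already wear a wrist Actigraph before and after.

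*Combined protocol and SAP*

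**What the plan says.** - **Purpose.** Section 4, Overview of study design, says the trial tests the programme "in promoting physical activity, pain, and sleep in older adults in comparison with a control group". Section 2 is narrower: its efficacy aim is "The preliminary efficacy of the study on pain and sleep outcomes", and its feasibility aim mentions pain, sleep and mood. Activity is not listed there.
- **Blinding.** The overview says "it is impossible to blind the group assignment from the participants and the research team".
- **Activity in both arms.** The baseline interview covers "depression, pain, fatigue, self-reported physical activity, Activity of daily living, self-reported sleep quality". The post-intervention meeting assesses level of physical activity among measures repeated by the same procedures. Measurement names instruments for sleep, pain, fatigue and function, but none for activity.
- **Actigraph in both arms.** At baseline, "After randomization, the research team will distribute an Actigraph to each eligible participant" with the instruction to "wear it on his/her non-dominant wrist day and night for 14 consecutive days". Later, "After the intervention or control period, a research team member will mail an Actigraph and a two-week sleep diary" for a further two weeks of wear.
- **Use of the device.** Measurement (which calls it an Actiwatch) says "We will use the Actiwatch to objectively assess nocturnal sleep in terms of total nocturnal sleep time", together with latency and wake after sleep onset. The intervention description also uses the baseline recording to build the circadian profile behind the personalised plan.
- **Smartwatch.** Steps and moderate minutes are described only within the intervention. The control condition includes no watch.
- **SAP 7.3.** It applies repeated-measures ANOVA (Time × Group) to the proposed outcomes and names no activity outcome.

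**The concern.** Activity is the presumed route to benefit: Section 3 argues that self-efficacy changes behaviour and that behaviour changes health. A reader of the results will want to know whether activity differed between arms, both to interpret a null pain or sleep result and to support a positive one.

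As written, that question would be answered by self-report in conditions that favour bias. Participants know their arm. The research team coaches the intervention arm every two weeks and also conducts the interviews, and only that arm is paid for meeting weekly exercise goals. The alternative is an activity measure chosen after the data are seen. A device record from both arms, which does not depend on what participants say, is already planned, but the plan does not say it will be read for activity.

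**Working it through.** The documents give no alpha, power, effect size, SD or dropout rate behind the sample of 20, so there is no stated figure to reproduce. The check traces each activity-related measure by arm, and then sizes what the unused recordings could deliver.

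**Trace**

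| Measure | Intervention | Control | Stated use |
|---|---|---|---|
| Self-reported activity | before and after | before and after | none named; no instrument |
| Smartwatch steps, moderate minutes | during the 12 weeks | not described | self-monitoring and coaching; Fitabase files stored |
| Wrist Actigraph | 2 weeks before, 2 weeks after | same | nocturnal sleep; baseline circadian profile for the plan |
| SPPB | yes | yes | balance and gait speed, which is capacity and not activity level |

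The follow-up activity item is not itself labelled self-report; that reading comes from the statement that the same procedures are followed. No row gives a named, device-based activity comparison between arms.

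**Wear already planned**
- Total: 20 participants × 2 periods × 14 days = 560 participant-days.
- With a stated daytime use (intervention-arm baseline, circadian profile): 10 × 14 = 140.
- Without one: 560 − 140 = 420, and 420/560 = 75%.

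**Precision of an Actigraph activity difference**

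Inputs: 1:1 allocation of 20 gives n = 10 per arm. Assumed: pre-post correlation r from 0.5 to 0.8, and loss of 2 per arm for n = 8. The 95% half-widths in SD units are:
- follow-up only: t(2n−2) × √(2/n)
- Time × Group change: t(2n−2) × √(2/n) × √(2(1−r))
- baseline-adjusted: t(2n−3) × √(2/n) × √(1−r²)

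For n = 10:
- follow-up only: 2.101 × 0.447 = 0.94
- change: 0.94 × 1 = 0.94 (r = 0.5); 0.94 × 0.632 = 0.59 (r = 0.8)
- adjusted: 2.110 × 0.447 × 0.866 = 0.82 (r = 0.5); 2.110 × 0.447 × 0.6 = 0.57 (r = 0.8)

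For n = 8:
- follow-up only: 2.145 × 0.5 = 1.07
- adjusted: 2.160 × 0.5 × 0.866 = 0.94 (r = 0.5); 2.160 × 0.5 × 0.6 = 0.65 (r = 0.8)

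**Chance that the interval excludes zero at a true difference of 0.5 SD (assumed)**

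The noncentrality is 0.5 / (√(2/n) × √(1−r²)) on 2n−3 df for the adjusted estimate. For n = 10 it is 1.29 (r = 0.5) and 1.86 (r = 0.8) on 17 df, giving 23.0% and 42.0%. The Time × Group change gives 18.5% and 38.7%. For n = 8 the adjusted figures are 19% and 34%.

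**What biased self-report could do**

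Take no true effect, n = 10 per arm, a two-sided 5% t-test on change scores, and an assumed differential reporting bias in SDs of change:

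| Bias (SD) | Chance of a significant difference |
|---|---|
| 0 | 5% |
| 0.25 | 8% |
| 0.5 | 19% |
| 0.8 | 40% |
| 1.0 | 56% |

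**The case against.** The strongest reply is that activity is not a declared efficacy outcome. Section 2 confines efficacy to pain and sleep, the concern rests on one overview sentence, and no listed objective fails. This stands as a limit on severity, but the overview still says activity is tested against control, and the plan does not say how.

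A second reply is that the remedy answers a different question. Follow-up wear begins once the calls and incentives have stopped, so a null result could not separate activity that never rose from activity that rose and lapsed. The interval would also be wide. Both points stand. They limit what the estimate can be used for, but it would still cover the same two weeks as the actigraphy sleep outcome.

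Three smaller points also stand:
- The 75% figure counts days with no stated daytime use. Those recordings still serve the sleep outcomes, so it is not a measure of harm.
- Wrist counts may miss some of the dumbbell and band work.
- Intervention-arm activity is already tracked during the programme, and SAP 7.2 could cover it as feasibility data. That gives no comparison with control.

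It can also be said that SAP 7.3 names no outcome individually, so the omission is general. That is true, but activity is worse placed than sleep or pain, whose instruments are at least named in Measurement.

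**Conclusion.** The concern holds. The plan presents activity as something tested against control, yet the only comparison it provides for is self-report in an unblinded trial, while device data from both arms have no named activity outcome. The plan should be changed, although the gap does not undermine the trial: the randomised pain and sleep comparison is not affected.

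The gain is a pre-specified, device-based estimate, wide but not open to reporting bias. It cannot serve as a test, because even a true 0.5 SD difference would exclude zero in fewer than half of such trials. The precision figures rest on the assumed correlations, loss and effect size. The conclusion about the gap rests only on the documents, reading the follow-up activity item as self-report and taking Actigraph and Actiwatch as the same wrist device.

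**What to change.** 1. In Measurement and SAP 7.3, name daytime Actigraph activity as a secondary outcome in both arms: mean waking activity count per valid day, with the valid-day rule fixed in advance.
2. Report the baseline-adjusted between-arm difference with a 95% confidence interval, as an estimate and not a test. Put the follow-up-only difference beside it, because baseline wear follows randomisation.
3. Instruct day-and-night wear at follow-up, as at baseline.
4. State that follow-up wear starts after week 12, so the result shows activity that persisted.
5. Name the self-report instrument and treat it as supportive.
6. Under SAP 7.2, describe weekly steps and moderate minutes from the stored Fitabase data in the intervention arm, to show the course of activity over the 12 weeks. There is no control arm for this, and it does not show the rise from baseline.

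The cost is wording in Measurement and SAP 7.2 and 7.3, one more read-out from files already collected, and one wear instruction. No new device, visit or participant is needed. The plan should also state the downsides: a wide interval, persistence only, and wrist counts that may miss resistance work. Items 5 and 6 are clarifications; the substance lies in items 1 to 4.
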